2.3.5. Site Inspections

Site visits will be conducted by the Sponsor or an authorized representative for inspection of study data, participants' medical records, and eCRFs. The Investigator will permit national and local Health Authorities, Sponsor monitors, representatives, and collaborators, and the IRBs/ECs to inspect facilities and records relevant to this study.

3. ADMINISTRATIVE STRUCTURE

See Section 4.1.2.

4. STUDY AND SITE CLOSURE

The Sponsor (or designee) has the right to close the study site or terminate this study at any time. Reasons for terminating the study may include, but are not limited to, the following:

- The incidence or severity of adverse events in this or other studies indicates a potential health hazard to participants.
- Participant enrollment is unsatisfactory.

The Sponsor will notify the Investigator and Health Authorities if the study is placed on hold, or if the Sponsor decides to discontinue the study or development program.

Study sites will be closed upon study completion. A study site is considered closed when all required documents and study supplies have been collected and a study-site closure visit has been performed.

The Investigator may initiate study-site closure at any time, provided there is reasonable cause and sufficient notice is given in advance of the intended termination.

Reasons for the early closure of a study site by the Sponsor or Investigator may include but are not limited to:

- Failure of the Investigator to comply with the protocol, the requirements of the IRB/IEC or local Health Authorities, the Sponsor's procedures, or GCP guidelines.
- Inadequate recruitment of participants by the Investigator.
- Discontinuation of further study treatment development.

Appendix 2 Adverse Events: Definitions and Procedures for Evaluating, Follow-up and Reporting

1. DEFINITION OF ADVERSE EVENTS

According to the E2A International Council on Harmonisation guideline for Good Clinical Practice, an **adverse event (AE)** is any untoward medical occurrence in a participant or clinical investigation participant administered a pharmaceutical product and which does not necessarily have to have a causal relationship with this treatment.

An AE can therefore be:

 Any unfavorable and unintended sign (including an abnormal laboratory finding), symptom, or disease temporally associated with the use of a medicinal product, whether or not considered related to the medicinal product.

Events Meeting the AE Definition:

- Deterioration in a laboratory value (hematology, clinical chemistry, or urinalysis) or other clinical test (e.g., ECG, angiography) that is associated with symptoms or leads to a change in study treatment or concomitant treatment or discontinuation from study treatment (see Appendix 3, Section 4).
- Exacerbation of a chronic or intermittent preexisting condition, including either an increase in frequency and/or intensity of the condition.
- New conditions detected or diagnosed after study treatment administration even though it may have been present before the start of the study.
- Adverse events that are related to a protocol-mandated intervention, including those that occur prior to assignment of study treatment (e.g., screening invasive procedures such as angiographies).

Events NOT Meeting the AE Definition:

- Any clinically significant abnormal laboratory findings or other abnormal safety
 assessments which are associated with the underlying disease, unless judged by
 the Investigator to be more severe than expected for the participant's condition.
- The disease/disorder being studied or expected progression, signs, or symptoms of the disease/disorder being studied, unless more severe than expected for the participant's condition.
- Medical or surgical procedure (e.g., endoscopy, appendectomy): the condition that leads to the procedure is an AE.
- Situations where an untoward medical occurrence did not occur (social and/or convenience admission to a hospital).

 Anticipated day-to-day fluctuations of preexisting disease(s) or condition(s) present or detected at the start of the study that do not worsen.

2. DEFINITION OF SERIOUS ADVERSE EVENTS

If an event is not an AE per definition above, then it cannot be a serious adverse event (SAE) even if serious conditions are met (e.g., hospitalization for signs/symptoms of the disease under study, death due to progression of disease).

An SAE is defined as any untoward medical occurrence that at any dose:

- Results in death.
- Is life-threatening.

The term "life-threatening" in the definition of "serious" refers to an event in which the participant was at risk of death at the time of the event; it does not refer to an event which hypothetically might have caused death if it was more severe.

• Requires inpatient hospitalization or prolongation of existing hospitalization (see Appendix 3).

In general, hospitalization signifies that the participant has been detained (usually involving at least an overnight stay) at the hospital or emergency ward for observation and/or treatment that would not have been appropriate in the physician's office or outpatient setting. Complications that occur during hospitalization are AEs. If a complication prolongs hospitalization or fulfills any other serious criteria, the event is serious. When in doubt as to whether "hospitalization" occurred or was necessary, the AE should be considered serious.

Hospitalization for elective treatment of a preexisting condition that did not worsen from baseline is not considered an AE.

Results in persistent or significant disability/incapacity

Disability means substantial disruption of the participant's ability to conduct normal life functions.

This definition is not intended to include experiences of relatively minor medical significance such as uncomplicated headache, nausea, vomiting, diarrhea, influenza, and accidental trauma (e.g., sprained ankle) which may interfere with or prevent everyday life functions but do not constitute a substantial disruption.

- Is a congenital anomaly/birth defect.
- Other significant events:

Medical or scientific judgment should be exercised in deciding whether SAE reporting is appropriate in other situations such as important medical events that may not be immediately life-threatening or result in death or hospitalization but may

jeopardize the participant or may require medical or surgical intervention to prevent one of the other outcomes listed in the above definition. These events should usually be considered serious.

Examples of such events include invasive or malignant cancers, intensive treatment in an emergency room or at home for allergic bronchospasm, blood dyscrasias or convulsions that do not result in hospitalization.

3. RECORDING OF ADVERSE EVENT AND/OR SERIOUS ADVERSE EVENT

When an AE/SAE occurs, it is the responsibility of the Investigator to review all documentation (e.g., hospital progress notes, laboratory reports, and diagnostics reports) related to the event.

The Investigator will then record all relevant AE/SAE information in the electronic case report form (eCRF).

It is **not** acceptable for the Investigator to send photocopies of the participant's medical records to Medical Monitor in lieu of completion of the eCRF.

There may be instances when copies of medical records for certain cases are requested by the Medical Monitor. In this case, all participant identifiers, with the exception of the participant number, will be redacted on the copies of the medical records before submission to the Medical Monitor.

The Investigator will attempt to establish a diagnosis of the event based on signs, symptoms, and/or other clinical information. Whenever possible, the diagnosis (not the individual signs/symptoms) will be documented as the AE/SAE.

3.1. ASSESSMENT OF SEVERITY

The Investigator will make an assessment of severity for each AE and SAE reported during the study and assign it to one of the categories provided in Table 1 below (as a guidance for assessing AE severity).

The terms "severe" and "serious" are not synonymous. Severity refers to the intensity of an AE (rated as mild, moderate, or severe, or according to a predefined grading criteria [e.g., National Cancer Institute Common Terminology Criteria for AEs criteria); the event itself may be of relatively minor medical significance (such as severe headache without any further findings).

Severity and seriousness need to be independently assessed for each AE recorded on the eCRF.

SAEs are required to be reported by the Investigator to the Sponsor immediately (i.e., no more than 24 hours after learning of the event).

Table 1 Adverse Event Severity Grading Scale

Severity	Description
Mild	Discomfort noticed, but no disruption of normal daily activity
Moderate	Discomfort sufficient to reduce or affect normal daily activity
Severe	Incapacitating with inability to work or to perform normal daily activity

Note: Regardless of severity, some events may also meet seriousness criteria. Refer to definition of a serious adverse event (see above).

3.2. ASSESSMENT OF CAUSALITY

Investigators should use their knowledge of the participant, the circumstances surrounding the event, and an evaluation of any potential alternative causes to determine whether or not an AE is considered to be related to the study treatment, indicating "yes" or "no" accordingly. The following guidance should be taken into consideration:

- Temporal relationship of event onset to the initiation of study treatment.
- Course of the event, considering especially the effects of dose-reduction, discontinuation of study treatment, or reintroduction of study treatment.
- Known association of the event with the study treatment or with similar treatments.
- Known association of the event with the disease under study.
- Presence of risk factors in the participant or use of concomitant medications known to increase the occurrence of the event.
- Presence of non-treatment-related factors that are known to be associated with the occurrence of the event.

4. FOLLOW-UP OF AES AND SAES

The Investigator is obligated to perform or arrange for the conduct of supplemental measurements and/or evaluations as medically indicated or as requested by the Medical Monitor to elucidate the nature and/or causality of the AE or SAE as fully as possible. This may include additional laboratory tests or investigations, histopathological examinations, or consultation with other health care professionals.

Assessments at the occurrence of a sight-threatening AE or events of Intraocular Inflammation are described in Section 8.9.5

If a participant dies during participation in the study or during a recognized follow-up period, the Investigator will provide the Sponsor with a copy of any post-mortem findings

(if available) including histopathology. New or updated information will be recorded in the originally completed eCRF.

The Investigator will submit any updated SAE data to the Sponsor within 24 hours of receipt of the information.

5. IMMEDIATE REPORTING REQUIREMENTS FROM INVESTIGATOR TO SPONSOR

Certain events require immediate reporting to allow the Sponsor to take appropriate measures to address potential new risks in a clinical trial. The Investigator must report such events to the Sponsor immediately; under no circumstances should reporting take place more than 24 hours after the Investigator learns of the event. The following is a list of events that the Investigator must report to the Sponsor within 24 hours after learning of the event, regardless of relationship to study treatment:

- Serious adverse events (see Section 2 in Appendix 2)
- Non-serious Adverse events of special interest (AESI)(see Section 8.3.6)
- Sight-threatening AEs (see Section 8.3.7
- Pregnancies (see Section 8.3.5)
- Medical device incidents (see Section 8.3.9 for details on medical device incidents).

The Investigator must report new significant follow-up information for these events to the Sponsor immediately (i.e., no more than 24 hours after becoming aware of the information). New significant information includes the following:

- New signs or symptoms or a change in the diagnosis.
- Significant new diagnostic test results.
- Change in causality based on new information.
- Change in the event's outcome, including recovery.
- Additional narrative information on the clinical course of the event.

Investigators must also comply with local requirements for reporting SAEs to the local Health Authority and IRB/EC.

5.1 REPORTING REQUIREMENTS OF SERIOUS ADVERSE EVENTS AND NON-SERIOUS ADVERSE EVENTS OF SPECIAL INTEREST

Events that Occur prior to Study Treatment Initiation

After informed consent has been obtained but prior to initiation of study treatment, only SAEs caused by a protocol-mandated intervention should be reported. The Clinical Trial Adverse Event/Special Situations Form provided to Investigators should be completed and submitted to the Serious Adverse Event Responsible immediately (i.e., no more than 24 hours after learning of the event).

Events that Occur after Study Treatment Initiation

For reports of SAEs, non-serious AESI (Section 8.3.6), and sight-threatening AES (Section 8.3.7) that occur after initiation of study treatment (Section 8.3.1), Investigators should record all case details that can be gathered immediately (i.e., within 24 hours after learning of the event) on the appropriate Adverse Event of Special Interest/ Serious Adverse Event eCRF form and submit the report via the EDC system. A report will be generated and sent to the Sponsor's Safety Risk Management department.

In the event that the EDC system is unavailable, the Clinical Trial Adverse Event/Special Situations Form provided to investigators should be completed and submitted to the Serious Adverse Event Responsible immediately (i.e., no more than 24 hours after learning of the event).

Once the EDC system is available, all information will need to be entered and submitted via the EDC system.

Reporting of Post-Study Adverse Events and Serious Adverse Events

If the Investigator becomes aware of any other SAE occurring after the end of the AE reporting period, and if the event is believed to be related to prior study treatment, the event should be reported directly to the Sponsor or its designee, either by faxing or by scanning and emailing the SAE Reporting Form using the fax number or email address provided to investigators.

5.2 REPORTING REQUIREMENTS FOR CASES OF ACCIDENTAL OVERDOSE OR MEDICATION ERROR

Accidental overdose and medication error (hereafter collectively referred to as "special situations"), are defined as follows:

- Accidental overdose: accidental administration of a drug in a quantity that is higher than the assigned dose
- Medication error: accidental deviation in the administration of a drug

Note: In some cases, a medication error may be intercepted prior to administration of the drug.

Special situations are not in themselves AEs, but may result in AEs. Each AE associated with a special situation should be recorded separately on the Adverse Event eCRF. Special situations and AEs (non-serious) associated with special situations need to be reported to Roche within 30 calendar days. If the associated AE fulfills seriousness criteria, the event should be reported to the Sponsor immediately (i.e., no more than 24 hours after learning of the event). For RO7200220 and ranibizumab, AEs associated with special situations should be recorded as described below for each situation:

- Accidental overdose: Enter the AE term. Check the "Accidental overdose" and "Medication error" boxes.
- Medication error that does not qualify as an overdose: Enter the AE term. Check the "Medication error" box.
- Medication error that qualifies as an overdose: Enter the AE term. Check the "Accidental overdose" and "Medication error" boxes.

In addition, all special situations associated with RO7200220 and ranibizumab, regardless of whether they result in an AE, should be recorded on the Adverse Event eCRF and should be recorded as described below:

- Accidental overdose: Enter the drug name and "accidental overdose" as the event term. Check the "Accidental overdose" and "Medication error" boxes.
- Medication error that does not qualify as an overdose: Enter the name of the drug administered and a description of the error (e.g., wrong dose administered, wrong dosing schedule, incorrect route of administration, wrong drug, expired drug administered) as the event term. Check the "Medication error" box.
- Medication error that qualifies as an overdose: Enter the drug name and "accidental overdose" as the event term. Check the "Accidental overdose" and "Medication error" boxes. Enter a description of the error in the additional case details.
- Intercepted medication error: Enter the drug name and "intercepted medication error" as the event term. Check the "Medication error" box. Enter a description of the error in the additional case details.

As an example, an accidental overdose that resulted in a headache would require the completion of two Adverse Event eCRF pages, one to report the accidental overdose and one to report the headache. The "Accidental overdose" and "Medication error" boxes would need to be checked on both eCRF pages.

6. EXPEDITED REPORTING TO HEALTH AUTHORITIES, INVESTIGATORS, INSTITUTIONAL REVIEW BOARDS, AND ETHICS COMMITTEES

The Sponsor will promptly evaluate all SAEs and non-serious AESI against cumulative product experience to identify and expeditiously communicate possible new safety findings to investigators, IRBs, ECs, and applicable Health Authorities based on applicable legislation.

To determine reporting requirements for single AE cases, the Sponsor will assess the expectedness of these events using the following reference documents:

- RO7200220:
 - use RO7200220 IB

Ranibizumab:

- use Lucentis® EU SmPC.

The Sponsor will compare the severity of each event and the cumulative event frequency reported for the study with the severity and frequency reported in the applicable reference document.

Reporting requirements will also be based on the Investigator's assessment of causality and seriousness, with allowance for upgrading by the Sponsor as needed.

Appendix 3 Procedures for Recording Adverse Events

Investigators should use correct medical terminology/concepts when recording adverse events (AEs) on the Adverse Event electronic case report from (eCRF). Avoid colloquialisms and abbreviations.

For the purposes of reporting events of infection and inflammation of the eye, the following terms and definitions should be used:

Iritis: the presence of inflammatory cells in the anterior chamber

The presence of aqueous flare alone will not constitute iritis but should be documented as an anterior chamber flare for AE reporting purposes.

- Iridocyclitis: the presence of inflammatory cells in both the aqueous and vitreous
- Vitritis: the presence of active inflammation in the vitreous, demonstrated by the presence of inflammatory cells (trace or greater)

Active inflammation in the vitreous should be clinically differentiated from cellular debris from prior episodes of inflammation, hemorrhage, or other causes.

 Endophthalmitis: diffuse intraocular inflammation predominantly involving the vitreous cavity but also involving the anterior chamber, implying a suspected underlying infectious cause

Note: Trace benign, aqueous pigmented cells visible on slit-lamp examination that are caused by dilation and are not red blood cells or white blood cells or the result of any ocular disorder should not be recorded as an AE.

Only one AE term should be recorded in the event field on the Adverse Event eCRF.

1. DIAGNOSIS VERSUS SIGNS AND SYMPTOMS

A diagnosis (if known) should be recorded on the Adverse Event eCRF rather than individual signs and symptoms (e.g., record only liver failure or hepatitis rather than jaundice, asterixis, and elevated transaminases). However, if a constellation of signs and/or symptoms cannot be medically characterized as a single diagnosis or syndrome at the time of reporting, each individual event should be recorded on the Adverse Event eCRF. If a diagnosis is subsequently established, all previously reported AEs based on signs and symptoms should be nullified and replaced by one adverse event report based on the single diagnosis, with a starting date that corresponds to the starting date of the first symptom of the eventual diagnosis.

2. ADVERSE EVENTS OCCURRING SECONDARY TO OTHER EVENTS

In general, AEs occurring secondary to other events (e.g., cascade events or clinical sequelae) should be identified by their primary cause, with the exception of severe or serious secondary events. However, medically significant AEs occurring secondary to an initiating event that are separated in time should be recorded as independent events on the Adverse Event eCRF. For example:

- If vomiting results in mild dehydration with no additional treatment in a healthy adult, only vomiting should be reported on the eCRF.
- If vomiting results in severe dehydration, both events should be reported separately on the eCRF.
- If a severe gastrointestinal hemorrhage leads to renal failure, both events should be reported separately on the eCRF.
- If dizziness leads to a fall and subsequent fracture, all three events should be reported separately on the eCRF.

All AEs should be recorded separately on the Adverse Event eCRF if it is unclear as to whether the events are associated.

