5.2 EXCLUSION CRITERIA

Participants are excluded from the study if any of the following criteria apply:

Medical Conditions

- 1. Any major illness or major surgical procedure within 4 weeks prior to Day 1
- 2. Any febrile illness within 1 week prior to screening or Day 1
- 3. Any stroke or myocardial infarction within 24 weeks prior to Day 1
- 4. Renal failure requiring renal transplant, hemodialysis, or peritoneal dialysis within 24 weeks prior to Day 1 or anticipated to require hemodialysis or peritoneal dialysis at any time during the study
- 5. Active malignancy within 1 year of screening except for appropriately treated carcinoma in situ of the cervix, non-melanoma skin carcinoma, and prostate cancer with a Gleason score of < 6 and a stable prostate-specific antigen (PSA) for > 1 year
- 6. History of other disease, metabolic dysfunction, physical examination finding, or clinical laboratory finding giving reasonable suspicion of a condition that contraindicates the use of either of the Investigational Medicinal Products (IMPs) or that might affect interpretation of the results of the study or renders the participant at high risk for treatment complications in the opinion of the Investigator
- 7. Any known hypersensitivity to any of the following compounds: fluorescein, biologic IVT agents such as Lucentis® (ranibizumab), Eylea® (aflibercept), Avastin® (bevacizumab), Beovu® (brolucizumab), any ingredient of the formulation used, dilating eye drops, or any anesthetics and *anti*microbial drops used
- 8. Evidence of HIV infection and/or positive human HIV antibodies; evidence of syphilis or tuberculosis and/or positive assay

Prior/Concomitant Therapy

- 9. Prior or concomitant periocular or IVT corticosteroids in the study eye:
 - a. For treatment naïve participants:
 - Received any prior or concomitant IVT corticosteroid treatment
 - b. For previously treated participants:
 - Received Triamcinolone within 16 weeks prior Day 1
 - Received Ozurdex® (dexamethasone IVT implant) within 16 weeks prior Day 1
 - Used ILUVIEN® or Retisert®(fluocinolone acetonide IVT implant) within 3 years prior Day 1

Note: Topical or IVT corticosteroids are allowed if required to treat AEs during the study.

- 10. Prior or concomitant IVT with anti-VEGF component in the study eye:
 - a. For treatment naïve participants:
 - Received any prior or concomitant IVT treatment with anti-VEGF component
 - b. For previously treated participants:

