4.6.2 Adverse Events

All verbatim AE terms will be coded using the latest version of Medical Dictionary for Regulatory Activities (MedDRA), and the incidence, severity, and seriousness will be summarized by treatment arm.

For safety analyses, unless otherwise specified, only treatment-emergent AEs will be included in the analyses. A treatment-emergent AE is defined as any new AE reported or any worsening of an existing condition on or after the first dose of study drug. Adverse events with missing onset date will be considered to be treatment emergent. Adverse events with partially missing onset date will also be included as treatment emergent when the month (if it was recorded) and the year occur on or later than the month and year of the study treatment start date.

Frequency tables, including participant incidence proportions by treatment arm, will be provided for the events listed below. In addition, graphical presentations will be included, as applicable. For ocular AEs, events in the study eye and fellow eye will be summarized separately.

- Ocular AEs and serious adverse events (SAEs)
- Non-ocular AEs and SAEs
- AEs leading to discontinuation of study treatment
- Treatment related ocular AEs and SAEs as determined by the Investigator
- Procedure related ocular AEs and SAEs as determined by the Investigator
- Intraocular inflammation (IOI)

- Cataract
- Elevated Intraocular Pressure (IOP)
- Infection/Endophthalmitis
- Retinal Detachment
- Retinal vascular occlusive disease

Adverse events associated with suspected or confirmed COVID-19 will also be provided.

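### A non-severe IOP rise found with, and clearly attributed to, intraocular inflammation may be recorded only as the inflammation and so be missing from the SAP's elevated-IOP table

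*Protocol*

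**What the plan says.** Protocol Appendix 3, Section 2 sets the recording rule. In general, "AEs occurring secondary to other events (e.g., cascade events or clinical sequelae) should be identified by their primary cause", and the same sentence adds "with the exception of severe or serious secondary events". Two further rules follow:

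- "medically significant AEs occurring secondary to an initiating event that are separated in time should be recorded as independent events", with no severity condition.
- "All AEs should be recorded separately on the Adverse Event eCRF if it is unclear as to whether the events are associated".

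The worked example of an event that is not entered separately is a mild one: "If vomiting results in mild dehydration with no additional treatment in a healthy adult, only vomiting should be reported on the eCRF".

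SAP 4.6.2 states: "Frequency tables, including participant incidence proportions by treatment arm, will be provided for the events listed below". Its list has separate lines for IOI, cataract, elevated IOP, infection or endophthalmitis, retinal detachment and retinal vascular occlusion. No rule in the SAP recovers an event that was recorded only under its cause.

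SAP 4.6.3 summarises IOP, slit-lamp and ophthalmoscopy results descriptively by arm and timepoint, including change from baseline in pre-dose IOP. It tabulates signs of IOI by grade, and retinal break or detachment. It names no count of participants with raised IOP. Protocol 9.3.3 adds the change in IOP from before to after dosing.

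**The concern.** The recording rule is written for general medicine; its examples are vomiting, gastrointestinal bleeding and a fall. SAP 4.6.2 treats eye events that can be causally linked as separate outcomes, each with its own incidence by arm. Where the two meet, an IOP rise that belongs to an episode of IOI can be counted on the IOI line alone.

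The loss need not be equal between arms. It is proportional to the amount of IOI, so an arm with more IOI loses more of its IOP rises and the arms look more alike on elevated IOP than they are. The design leaves room for such a difference: Arm A receives two intravitreal injections at each dosing visit, and Arm B receives one injection and a sham without a needle (Protocol Sections 4.1 and 6.1, Table 3). Elevated IOP is one of the local risks that the SAP chose to compare between arms.

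**Working it through.** **Step 1. Apply the full recording rule to the possible cases.**

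| Event in an eye with IOI | Part of Appendix 3, Section 2 that applies | Entered as its own event? |
|---|---|---|
| Severe or serious IOP rise | Severe or serious exception | Yes |
| Medically significant IOP rise at a later visit, for example after steroid treatment | Time-separation rule | Yes |
| Medically significant cataract first seen at a later visit | Time-separation rule | Yes |
| IOP rise that could be due to the IOI or to something else, such as the injection | Unclear-association rule | Yes |
| Non-severe, non-serious IOP rise found with the IOI and clearly attributed to it | General rule | Possibly not |

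The last row is the gap. Later events fall into it only if they are clearly linked and not judged medically significant.

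**Step 2. Look for another output that restores the count.** The IOP summaries in SAP 4.6.3 and Protocol 9.3.3 do not depend on how an adverse event is coded. As specified, they describe values and changes, not the number of participants who had a raised reading. The secondary endpoint on abnormalities in ophthalmological assessments (Protocol Section 3, Table 2) does not say what counts as an IOP abnormality. The compensation is partial.

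**Step 3. Size.** The documents state no figure to reproduce, and their readable text gives no rate of IOI or of IOP rise. Every rate below is an assumption.

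Inputs:
- n per arm: 90 (SAP 3.1) and 110 (midpoint of the 105 to 115 in the Protocol synopsis).
- IOI rate p, higher arm vs lower arm: 2% vs 1%, 5% vs 1%, 10% vs 2% (assumed).
- Share s of IOI cases with an IOP rise: 10% to 30% (assumed).
- Share f of those rises entered only as IOI: 25% to 100%, the same in both arms (assumed).
- An affected participant has no other recorded IOP event (assumed; if some do, the loss is smaller).

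Formulas:
- Participants lost from the elevated-IOP table in one arm = n × p × s × f.
- Understatement of the between-arm difference = (p higher − p lower) × s × f. The sample size cancels.

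| IOI rates | s | f | Lost, n = 90 (higher, lower arm) | Lost, n = 110 (higher, lower arm) | Understatement (points) |
|---|---|---|---|---|---|
| 2% vs 1% | 10% | 25% | 0.05, 0.02 | 0.06, 0.03 | 0.03 |
| 5% vs 1% | 30% | 25% | 0.34, 0.07 | 0.41, 0.08 | 0.30 |
| 5% vs 1% | 30% | 100% | 1.35, 0.27 | 1.65, 0.33 | 1.20 |
| 10% vs 2% | 30% | 25% | 0.67, 0.14 | 0.82, 0.17 | 0.60 |
| 10% vs 2% | 30% | 100% | 2.70, 0.54 | 3.30, 0.66 | 2.40 |

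Largest case: (0.10 − 0.02) × 0.30 × 1.00 = 0.024, or 2.4 points. With f = 0.25 it is 0.6 points. With equal IOI rates and equal f it is zero.

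**Step 4. Scale.** Take two incidences of 5% (assumed) and the 90% level that the Protocol uses for efficacy. The half-width for their difference is 1.645 × √(2 × 0.05 × 0.95 / n), which is 5.3 points at n = 90 and 4.8 points at n = 110.

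**The case against.** The strongest case on the other side is that the exceptions cover most of what matters. The only folded example in Appendix 3 is mild and untreated, and the fall-and-fracture example records all three events. In diabetic eyes injected every four weeks, an IOP rise often has a competing explanation, and then it must be recorded separately. The IOI itself is still counted, so an excess of inflammation in one arm stays visible. Examination findings are collected at every visit whatever the coding. All of this stands, and it keeps the point small.

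It does not close the gap. When the IOP rise is found with the IOI and the link is clear, none of the exceptions applies, and no planned output names how many participants had a raised IOP.

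Three stronger readings are tempting, and the documents do not support them:

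- A reader might infer that non-severe IOP rises and cataracts following IOI are lost as a class. The time-separation and unclear-association rules have no severity condition, so a later cataract would mostly be recorded in its own right.
- A reader might infer from the Protocol 5.2 note, "Topical or IVT corticosteroids are allowed if required to treat AEs during the study", that steroid-related IOP rises are lost too. Such a rise comes after both the IOI and its treatment, so if medically significant it is recorded independently.
- A reader might infer that SAP 4.6.3 offers only mean IOP. It specifies descriptive summaries and graphs as applicable, which is broader, though still without a stated participant count.

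**Conclusion.** The point holds in a narrow form. A non-severe, non-serious IOP rise that is found together with IOI and clearly attributed to it may be missing from the elevated-IOP table in SAP 4.6.2. Any resulting bias in the comparison is conditional: it needs a difference in IOI between arms, and the readable text gives no rates that would show one. If the difference exists and folding is equally likely in both arms, the bias runs towards making the arms look alike.

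Under the assumed rates the understatement is 0.03 to 2.4 percentage points, with 0.05 to 3.3 participants lost in the arm with more IOI. The top of that range requires every such rise to be folded. With 25% folded, which the exceptions make more realistic than 100%, the maximum is 0.6 points, well inside a 90% half-width of about 5 points. A reader should therefore not conclude that the plan hides a safety difference. It leaves a small, avoidable undercount in one listed safety table.

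**What to change.** Either of these closes the gap, and both can be done.

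1. Add to Protocol Appendix 3, Section 2, and to the eCRF completion guide: elevated IOP, cataract and retinal vascular occlusive events in the study eye are entered as their own adverse event even when judged secondary to inflammation, with the initiating event named. Each participant is counted once per category. These are the SAP 4.6.2 categories that can be secondary to IOI and for which SAP 4.6.3 names no participant tabulation.
2. Add to SAP 4.6.3 a by-arm count of participants with any measured IOP at or above a pre-specified analysis level. The 30 mmHg in the Schedule of Activities footnote on post-treatment IOP is one candidate already in the documents; here it would serve only as a cut for tabulation. Show pre-dose and post-dose readings separately, because Arm A receives two injected volumes per dosing visit and Arm B one.

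The second option uses data already scheduled at every visit, so it still works if adverse event recording is too far advanced to change. The cost is a few extra adverse event pages or one extra table. Under the first option one episode may appear in two categories, which a table footnote should say. Neither option affects treatment or the efficacy analysis.
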